The present clinical study proposes to identify atherosclerotic transcriptomic patterns from a whole blood sample. Likewise, as a secondary analysis, we will explore the ability of the algorithm to determine the presence of aortic disease and pro-inflammatory cardiometabolic alterations such as hepatic steatosis and surrogate markers of epicardial fat inflammation.

4. Background and Rationale

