1. To classify transcriptomes according to the presence and extent of coronary calcification by noncontrast cardiac CT.
2. Train artificial intelligence algorithms with information from the transcriptome to recognize the presence and extent of calcification in coronary arteries.

-
3. To determine the degree of diagnostic accuracy of the method to detect the presence and extent of coronary calcification non-invasively.

Secondary objectives

1. To determine the degree of diagnostic accuracy of the method to detect the presence and extent of:
 - Aortic
 - calcification Aortic valve calcification
 - Hepatic steatosis
 - Volume of epicardial fat
 - Volume of high-density epicardial fat (upper quartile)
 - Enlargement of cardiac cavities To
2. To explore differences in transcriptomics of peripheral blood between patients who did and did not develop a CV event during follow-up.
3. To explore different electrocardiographic patterns according to the results of cardiac CT and peripheral blood transcriptomics.
4. Generate a polygenic risk score (PRS) from the transcriptome and/or exome sequencing and associate it with the transcriptome and coronary calcification.

7. Methods

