8.5. Analysis of cardiac CT

The presence of CAC and its extension will be evaluated using both ordinal variables (number of segments with CAC and number of affected vessels, and qualitatively: absence, mild, moderate, and severe; and the number of coronary segments with calcification) as continuous variables (Agatston units). The presence and extension of calcifications at the level of the aortic valve and the thoracic aorta (Agatston units) will also be evaluated independently. The extent of aortic calcification will be evaluated in sections that include from the bifurcation of the pulmonary artery as the upper limit to the diaphragm as the lower limit.

Quantitative analysis of SCC will be performed using dedicated software (HeartBeat-CS, Philips Healthcare, Best, The Netherlands). Finally, the volume and density of epicardial fat will be calculated by evaluating the volume of tissue with a density between -190 and -30 HU located in the area between the epicardium and the pericardium, the bifurcation of the pulmonary artery as the upper limit, and the diaphragm as lower limit.

Finally, the density of the hepatic parenchyma will be calculated through a region of interest >100 mm² at the level of the right and splenic lobes. From these measurements, the presence of hepatic steatosis will be defined from a quotient of less than 1.

At least 20% of the participants (randomly selected) will have a double reading of the main outcome of the study (presence or extent of CACs). This reading will be carried out by an expert external to the group of researchers of the study and blind to the first reading. In case of disagreement, consensus will be sought between the two experts. The aim of this process is to enhance the internal validity of the study.

The epicardial fat volume analysis will be performed by experts from the University of Palermo (Italy).

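### Accuracy for the high-density epicardial fat volume is confounded by the amount of fat, so on its own it is not specific evidence on epicardial fat inflammation

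*Combined protocol and SAP*

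**What the plan says.** The closing paragraph of the introduction, just before section 4, announces a secondary exploration of "hepatic steatosis and surrogate markers of epicardial fat inflammation". It does not say which measurement is the marker.

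Section 6, secondary objective 1, is framed as "To determine the degree of diagnostic accuracy of the method to detect the presence and extent of" a list of CT findings. Two of these concern epicardial fat: "Volume of epicardial fat" and "Volume of high-density epicardial fat (upper quartile"). Both are worded as volumes.

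Section 8.5 states that "the volume and density of epicardial fat will be calculated by evaluating the volume of tissue with a density between -190 and -30 HU". It gives no cut-off for high density, no fraction and no indexing to total volume. It adds that "The epicardial fat volume analysis will be performed by experts from the University of Palermo (Italy"), which mentions volume only.

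Section 9.4 lists general accuracy measures and an AUC. It contains no adjustment for total fat volume and no comparison with a model based on it.

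**The concern.** Inflammation is to be inferred from how dense the fat is, but the listed target measures how much dense fat there is. Two people whose fat has the same density, with 20% of it classed as dense, and total volumes of 60 and 180 mL would have 12 and 36 mL on this target. That is a threefold difference with no difference in density.

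An algorithm whose blood signature reflects adiposity alone could then be credited with two findings: that it detects epicardial fat volume, and that it detects epicardial fat inflammation. The second credit would not be earned, and nothing in the planned analysis would reveal this.

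**Working it through.** **Inputs from the documents.** The two targets (section 6), the -190 to -30 HU window (section 8.5) and the AUC as accuracy measure (section 9.4). The documents give no figure for this target: no mean, no SD, no dense fraction and no correlation. There is therefore no plan figure to reproduce, and every variance below is an assumption shown as a range.

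**Step 1: identity.** Let V be total volume, f the dense fraction and H the high-density volume. Then H = V × f. At fixed f, H is proportional to V. This needs no assumption.

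**Step 2: what *upper quartile* may mean.** The text does not say.
- *The densest quarter of each patient's own voxels.* H = 0.25 × V, correlation 1: an exact duplicate of total volume.
- *The top quarter of the HU window.* The window is 190 − 30 = 160 HU wide and a quarter is 40 HU, so the band is -70 to -30 HU. H = V × f, with f varying between patients.
- *The top quarter of patients on H.* The same H, turned into a yes/no label.

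**Step 3: how strongly H follows V.** Assume V and f lognormal, with log-scale SD s = √ln(1 + CV²) and log-scale correlation ρ. Then

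corr(log V, log H) = (s_V + ρ s_f) / √(s_V² + s_f² + 2ρ s_V s_f).

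For CVs of 40% and 25%: s_V = √ln 1.16 = 0.385 and s_f = √ln 1.0625 = 0.246. With ρ = 0 the correlation is 0.385 / √(0.148 + 0.061) = 0.84.

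**Step 4: AUC by simulation.** The label is H in the top quartile. The grid is volume CV 30, 40, 50% by fraction CV 15, 25, 35%. The table shows the centre and the two extreme cells.

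| CV of V / CV of f | ρ | corr(log V, log H) | AUC, V alone | AUC, f alone | Top quarter of H also in top quarter of V |
|---|---|---|---|---|---|
| 30% / 35% | 0 | 0.65 | 0.82 | 0.87 | 57% |
| 40% / 25% | 0 | 0.84 | 0.92 | 0.76 | 71% |
| 50% / 15% | 0 | 0.95 | 0.98 | 0.64 | 84% |
| 30% / 35% | -0.6 | 0.31 | 0.65 | 0.78 | 39% |
| 40% / 25% | -0.6 | 0.77 | 0.88 | about 0.52 | 65% |
| 50% / 15% | -0.6 | 0.95 | 0.98 | 0.34 | 85% |

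Under independence, volume alone spans 0.82-0.98 and the fraction alone 0.64-0.87. At ρ = -0.6, volume alone spans 0.65-0.98. Where volume varies much more than the fraction, H can then run against density (fraction-only AUC below 0.5).

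A wider grid (fraction CV 10-50%, ρ from 0 to -0.6) gives log correlations from 0.03 to 0.98. The correlation is at least 0.74 whenever the fraction CV is 20% or less.

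**Step 5: the same check on the fraction.** With ρ = 0, total volume alone has an AUC of 0.50 for the top quartile of f, but only because independence was assumed. With ρ = -0.3 and -0.6 it is about 0.36 and 0.21: volume predicts the fraction in reverse.

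**The case against.** The strongest reply is that the target is openly labelled a volume, and that section 8.5 plans to calculate density as well. The link to inflammation is the reader's inference. The total amount of dense fat is also a defensible target for a blood test: section 4.4 argues that blood cells respond to signals from the tissues they perfuse, and more dense tissue may send more signal. This stands as a reason to keep the absolute volume. It does not supply a density target, because no objective is tied to the planned density measure and no other listed item fits the inflammation aim.

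A second reply is that the wording could mean patients in the upper quartile of density, in which case the label would not be an amount. The list is visibly garbled, so this cannot be excluded. As printed, however, the item is a volume, and the ambiguity itself needs resolving.

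A reader might go further and infer that the item largely repeats total volume, that it cannot show inflammation, or that its top quarter is simply the people with the most fat. The documents do not support these readings. How far it repeats total volume depends on variances and a correlation that are not given, except under the own-voxel reading, where duplication is exact. The fraction alone reaches up to 0.87 for the same label, and in one cell beats volume (0.87 against 0.82). Under independence, 57-84% of the top quarter on dense volume are also in the top quarter on total volume, so 16-43% are not.

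Finally, this is one item in an exploratory secondary list, and no test or decision depends on it. That limits the weight of the point but does not remove it.

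**Conclusion.** The point holds in a limited form. As worded, the target mixes amount and density, and the plan contains nothing to separate them. Good accuracy on it would not be specific evidence on inflammation, although it may carry a density signal.

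The structural part (H = V × f, with no normalisation and no comparison) follows from the text alone. The size does not. A volume-only AUC of 0.82-0.98 rests on lognormal quantities, the assumed CVs and independence, and the lower end falls to 0.65 if the fraction decreases as volume rises. That this item is the intended inflammation marker is an inference from the introduction. The primary objective is unaffected.

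**What to change.** In sections 6 and 8.5:

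1. State the HU cut-off for high density, and say whether *upper quartile* refers to the HU window, to each patient's voxels or to patients.
2. Add the high-density fraction (high-density volume divided by total epicardial fat volume) or mean epicardial fat attenuation in HU. Make this the density target on which any conclusion about inflammation rests.
3. Keep the absolute high-density volume, but report the algorithm's accuracy for it alongside, and beyond, a model that uses total volume only.
4. Report the correlation between the fraction and total volume. Do not assume that the fraction is independent of amount.
5. State that the external readers deliver density as well as volume.

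The cost is a few lines of text, a little more analysis and one more exploratory secondary target. Volume and density are already planned from the existing scan, so no new patient procedure is needed.

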7.1. Study Design

This trial will be a prospective observational study. A convenience sample will be carried out to include 800 patients who attend the ENERI Medical Institute, La Sagrada Familia Clinic, to undergo a cardiac CT without contrast (coronary calcium score), either for a medical indication or volunteers to an assessment of cardiovascular risk. The study will have a baseline stage in which a clinical evaluation will be performed, blood samples will be drawn for transcriptome analysis and laboratory analysis. Then, a DNA sample

obtained by swabbing the buccal mucosa will be taken. Subsequently, a non-contrast gated cardiac CT will be performed to assess the presence and extent of coronary calcification and other results of interest. At the end of patient enrollment, biological samples will be sequenced for in silico evaluation of the results. Finally, a 5-year clinical (telephone) follow-up will be carried out to collect data on the incidence of fatal and non-fatal cardiovascular events.

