5.2. Preliminary studies

We previously developed a clinical protocol with the aim of perfecting the methodology that will be used in this study. The initial goal was to develop blood collection, RNA isolation, library generation for sequencing, and RNA sequencing. Briefly, the preliminary results of these steps, performed on 540 samples from 3 different studies, are described below.

First, a robust methodology was established to obtain an RNA sample from peripheral whole blood (without cell separation). Samples were collected in PaxGene RNA tubes through antecubital vein puncture. No adverse effects were observed in this procedure. Samples were stored at -20°C until RNA extraction. This step was performed through the use of a specific kit (Thermo-Fischer). As a result, it was possible to consistently obtain RNA samples in sufficient quantities for sequencing in all cases. Then, the library was built, a process in which the RNA is transformed into cDNA (complementary DNA), from which the RNA corresponding to ribosomes and globin are extracted, fragmented, and finally the adapters are added at the ends. Again, the library construction was developed in a robust way for all the analyzed samples.

Subsequently, RNA sequencing was performed at a depth of 100 million reads. Between 20 and 25 thousand genes expressed in peripheral blood were detected in all the samples (n=540). In a series of patients, computed tomography was performed to determine the degree of calcification of the coronary arteries (Coronary Calcium Score, CCS). An analysis of gene expression in peripheral blood was performed and genes related to the degree of coronary calcification were found.

[figure not shown]

Figure 3: Preliminary results. We analyzed 38 samples from patients who had coronary calcium measured. The left panel shows the result of a PCA analysis where a moderate but significant reduction in dimensionality is found based on the extent of coronary calcium. The heatmap shows the differentially expressed genes between the two groups.

6. Study Objectives

Primary Objective

The primary objective of the study is to evaluate the diagnostic accuracy of peripheral whole blood transcriptomes analyzed by an artificial intelligence algorithm to detect the presence and extent of coronary calcification in individuals without a history of known cardiovascular disease.

Specific Primary Objectives

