7.2. Study Population

7.3. Inclusion Criteria

- Men and women between 30 and 75 years attending the institution for a non-contrast cardiac CT scan (coronary calcium score) either by medical indication or voluntary for cardiovascular risk assessment.
- Signature of informed consent form

7.4. Exclusion criteria.

- Previously known chronic renal or hepatic insufficiency.
- Active chronic lung disease, defined as: exacerbated asthma, exacerbated COPD, or pulmonary fibrosis.
- Active and/or previous cardiovascular disease, defined as: previous acute myocardial infarction, stable or unstable angina, cerebrovascular accident, history of vascular interventions (coronary or other territory), heart failure, severe cardiomyopathies or valvulopathies.
- Uncontrolled hyper or hypothyroidism.
- Suprarrenal insufficiency.
- Previous surgeries in the last 3 months.

-
- Severe trauma in the last 6 months, defined as one that involved bone fractures and/or surgical interventions.
 - Known active cancer disease or under treatment (acute or preventive), or history of cancer disease without criteria for cure.
 - Known autoimmune disease active or in treatment.
 - Ongoing pregnancy, postpartum period of less than 12 months or breastfeeding.
 - Other serious illness with an estimated life expectancy of less than 12 months (according to the investigators).
 - Temperature greater than 37.5°C recorded by a thermometer or any acute infection caused by viruses or bacteria confirmed by a health professional in the previous 30 days.
 - Pathologies under immunosuppressive treatment

8. Procedures

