8.1. Eligibility and informed consent

Patients will be recruited at the ENERI Medical Institute and at the outpatient clinics of the “La Sagrada Familia” clinic. Patients who meet the eligibility criteria will be approached by the main investigator or one of the study collaborators and the characteristics of the procedure to be performed, the risks of the associated procedures and the scope of the research to be carried out will be explained to them. After providing the necessary information and answering the questions of the participants, they will be formally invited to sign the informed consent.

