9.3. Calculation of the sample size

The calculation of the number of patients to demonstrate a positive effect for the use of peripheral blood transcriptomics for the diagnosis of the presence of severe coronary calcification is carried out based on previous experiences by the group of researchers. There is still no standardized methodology in the medical literature to perform the sample calculation of this type of analysis, since it is very recent and is in the exploration phase. Studies *silico* carried out by this group of researchers and the preliminary clinical studies carried out previously, it was observed that at least a sample of 800 patients is necessary for a robust training of the artificial intelligence algorithm that detects transcriptional differences between patients with or without a solid tumor. (for example, breast tumor). Therefore, 800 patients will be included based on the minimum number necessary to perform an adequate training of an artificial intelligence algorithm.

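### The accuracy study uses a convenience sample with no rule for whom to approach and no log of those not enrolled, so selection could bias accuracy in either direction

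*Combined protocol and SAP*

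**What the plan says.** The primary objective (section 6) is to "evaluate the diagnostic accuracy of peripheral whole blood transcriptomes analyzed by an artificial intelligence algorithm" for the presence and extent of coronary calcification. Section 9.4 measures this by sensitivity, specificity and AUC, among others.

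On sampling, section 7.1 states: "A convenience sample will be carried out to include 800 patients". Section 7.3 defines the source population as men and women aged 30 to 75 "attending the institution for a non-contrast cardiac CT scan (coronary calcium score) either by medical indication or voluntary for cardiovascular risk assessment". Section 8.1 says "Patients will be recruited at the ENERI Medical Institute and at the outpatient clinics" of a named clinic, and "Patients who meet the eligibility criteria will be approached by the main investigator or one of the study collaborators".

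No section calls enrolment consecutive or random, sets an order of approach, or provides for a log of people screened, not approached or refusing. The procedures manual in section 9.2(c) is to cover the baseline questionnaire, blood extraction and follow-up; a screening log is not named. Section 9.4 plans neither a participant flow nor accuracy by calcification category.

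**The concern.** Sensitivity, specificity and AUC belong to a test in a given population. If mild calcification is harder to detect than severe, the share of mild cases among the calcified drives sensitivity and AUC. The make-up of the uncalcified group affects specificity in the same way. A convenience sample leaves that mix to circumstance.

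People can be selected on what is visible before the scan: age, risk factors, and whether they come by medical indication or as volunteers. If those enrolled lean towards evidently high-risk patients and very healthy volunteers, accuracy looks better with no better algorithm. If they lean towards people with borderline disease, it looks worse. Without a record of who was eligible but not enrolled, a reader cannot judge how far the 800 represent the people attending for the scan.

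This matters for the stated purpose. Section 4.1 motivates the work by early detection in people without symptoms, where mild disease is important.

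**Working it through.** **The plan's own figure.** The 800 cannot be reproduced from a formula. Section 9.3 gives no alpha, power, prevalence, target accuracy or precision; its reasoning is "Therefore, 800 patients will be included based on the minimum number necessary to perform an adequate training of an artificial intelligence algorithm". The point here concerns how the 800 are obtained, and changing that leaves the number as it is.

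**What the sections say when read together.**
- Section 7.1 names the method as convenience, which does not commit the study to inviting all comers.
- Section 8.1 identifies who makes the approach and is silent on whom they approach. Read alone, it could mean that everyone eligible is approached.
- Section 7.1 puts the scan after the clinical evaluation, blood draw and swab: "Subsequently, a non-contrast gated cardiac CT will be performed to assess the presence and extent of coronary calcification". The result of that scan therefore cannot drive selection.
- Section 7.3 draws everyone from people attending for one type of scan under one set of criteria. This is not a case-control design, and a consecutive series is a natural option.

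**Illustration of a spectrum shift. All inputs are assumed; none is in the documents.** Let the algorithm's score be normal with variance 1 and mean 0 without calcification, 0.5 with mild and 1.2 with moderate or severe calcification. AUC against the uncalcified is Φ(δ/√2):
- mild: Φ(0.5/√2) = Φ(0.354) = 0.638
- moderate or severe: Φ(1.2/√2) = Φ(0.849) = 0.802

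The overall AUC is the average weighted by share of calcified patients:
- mild share 60%: 0.6 × 0.638 + 0.4 × 0.802 = 0.704
- mild share 50%: 0.5 × 0.638 + 0.5 × 0.802 = 0.720
- mild share 40%: 0.4 × 0.638 + 0.6 × 0.802 = 0.736

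Moving from 60% to 40% requires moderate or severe cases to be enrolled at (60/40) ÷ (40/60) = 2.25 times the rate of mild ones, and adds about 0.03.

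**The opposite direction.** If mild cases were enrolled at 2.25 times the rate of the others, the odds of mild become 1.5 × 2.25 = 3.375, a share of 3.375/4.375 = 77.1%. The AUC is 0.771 × 0.638 + 0.229 × 0.802 = 0.676, a loss of about 0.03.

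**Range under a wider assumed gap.** With means 0, 0.5 and 1.5, the severe AUC is Φ(1.5/√2) = 0.856. Raising the severe share of the calcified from 0.3 to 0.6 moves AUC from 0.703 to 0.769, and sensitivity at 80% specificity from 0.48 to 0.59. Over severe shares of 0.2 to 0.8, AUC runs from 0.682 to 0.812.

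**No-effect case.** If mild and severe cases both have mean 1.0, AUC is Φ(1/√2) = 0.760 whatever the mix.

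The illustration shows that the mix can matter. It does not show that it will, or in which direction.

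**The case against.** A reader might infer that investigators hand-pick clear-cut patients, so that accuracy will be overstated. The documents do not support this. Section 8.1 gives the investigators the task of approaching patients and does not describe a choice among them. The scan comes after enrolment, so selection could act only through imperfect proxies. Section 7.4 excludes angina, heart failure and earlier cardiovascular disease, which narrows selection on symptoms. Convenience could as easily favour readily available low-risk volunteers. Nor do the documents mention a scan list; that scheduled attenders can be identified in advance is a reasonable assumption, not a stated fact.

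The effect may also be modest beside sampling error. Section 5.1 describes validating with 10 or 20% of samples. If that applied here (80 or 160 people), with an assumed 50% prevalence of calcification and AUC of 0.70, the Hanley-McNeil standard error is about 0.06 or 0.04, which exceeds the illustrated 0.03. That stands, but a systematic shift does not average out as random error does.

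It would also be too strong to say that a shifted mix could never be seen. Section 8.5 records calcification as absent, mild, moderate or severe and in Agatston units, and section 8.2 records risk factors, so the achieved mix will be visible. What those data cannot show is how the enrolled differ from the eligible people who were not enrolled.

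Finally, the method is openly declared, and section 9.3 describes the field as exploratory. Disclosure is to the plan's credit, but does not make the sample representative.

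**Conclusion.** The point holds in a limited form. A diagnostic-accuracy study is planned on a declared convenience sample, with no rule for approaching eligible people and no log of those missed. That leaves sensitivity, specificity and AUC open to bias from the calcification spectrum, in either direction.

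The size cannot be derived from the documents. The shifts of about 0.03 in AUC, and the wider range under the second set of means, rest wholly on assumed score distributions and assumed selection ratios, and fall to zero if detectability does not depend on severity. Neither deliberate choice by investigators nor overstated accuracy is established. The change is still worth making because consecutive invitation is a better method at small cost, and because people missed during recruitment cannot reliably be logged afterwards. If the sponsor already means to approach everyone eligible, the same edit makes the text say so.

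**What to change.** In sections 7.1 and 8.1, replace the convenience sample with consecutive invitation, before the scan, of every eligible person scheduled for a calcium-score CT. The rule should cover people met at the institute and those met "at the outpatient clinics of the “La Sagrada Familia” clinic". Invitation should come early enough to allow the 8-hour fast that section 8.2 requires before the blood draw.

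Have the staff who already obtain consent keep a log of people attending, eligible, invited and enrolled, with age, sex, referral route (medical indication or volunteer) and reason for non-enrolment.

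In section 9.4, add three items: the participant flow, a comparison of enrolled with non-enrolled people on the logged items, and accuracy by the calcification categories already recorded under section 8.5.

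The cost is protocol wording, a short log, and possibly slower enrolment because slots can be filled less freely. The sample size stays at 800. Consecutive invitation does not remove self-selection by volunteers or by referral, which is why the log and the comparison should carry the referral route.

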8.3. Sample processing and sequencing

Blood samples will be processed after extraction using commercial kits for RNA extraction. Subsequently, the *library*, a procedure by which the transformation of the RNA sample into short cDNA chains for sequencing is known. For this procedure, the commercial TruSeq-RiboZero-GlobinFree kit (Illumina) will be used. Subsequent sequencing (without ribosomal RNA and globin) will be performed by an external sequencing service provider. A sequencing with a read depth of at least 100 million reads will be requested.

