9.1. Confidentiality of the data

The data of the patients will be collected anonymously from the moment of signing the informed consent. To do this, a representative code of the patient will be created, which will include the initials of the study, followed by a hyphen and the inclusion number. The clinical documentation of the patient and the tube containing the blood of the patients or control subjects will contain only this information. The informed consent will be kept in a different location from the clinical information and under lock and key.

The transcriptomics data will remain anonymized and will receive the name designated at the time of inclusion in the study. The data will be deposited and protected on outsourced servers in compliance with the European regulations of the General Data Protection Regulation (GDPR). AWS is currently used to safeguard the information.

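### The plan has no random allocation of samples to library and sequencing batches, no batch record and no batch-wise validation, so any link between batch and coronary calcification could inflate the accuracy estimate unseen

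*Combined protocol and SAP*

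**What the plan says.** On order of events, section 7.1 puts the scan in the baseline stage: "Subsequently, a non-contrast gated cardiac CT will be performed to assess the presence and extent of coronary calcification and other results of interest". Sequencing comes later: "At the end of patient enrollment, biological samples will be sequenced for in silico evaluation of the results". Section 9.3 fixes the number: "Therefore, 800 patients will be included based on the minimum number necessary to perform an adequate training of an artificial intelligence algorithm".

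On laboratory work, section 8.3 names commercial extraction and library kits and a depth of 100 million reads or more per sample. It adds: "Subsequent sequencing (without ribosomal RNA and globin) will be performed by an external sequencing service provider". Section 8.4 lists quality control, alignment and counting, then proprietary transformations whose content is not given, then a supervised neural network that takes coding, non-coding, circular and microbiome RNA. Section 8.2 allows two tube types and two routes of storage before freezing.

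On coding, section 9.1 gives each patient a code "which will include the initials of the study, followed by a hyphen and the inclusion number". The clinical record and the blood tube "will contain only this information".

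On validation, section 5.1 describes the group's general method, in which 10% or 20% of a cohort is used to validate. Section 9.4 specifies no split for this study.

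No section mentions plates, runs, allocation to batches, batch identifiers, batch correction or a check of CAC against batch. The one random selection in the plan is the subsample for the second CT reading in section 8.5, and the one statement of blinding concerns that second reader: "This reading will be carried out by an expert external to the group of researchers of the study and blind to the first reading". The manual of procedures in section 9.2 covers the questionnaire, blood extraction and follow-up, and does not list library or sequencing work.

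**The concern.** Eight hundred samples at 100 million reads make 80 billion reads. The plan does not say how many plates or runs that takes, but more than one is close to certain. Expression data differ between batches for technical reasons, and a network given every transcript can use such differences if they track the label.

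The plan leaves a route by which they could. The sample is a convenience mix of referred patients and volunteers from two recruitment settings, and nothing holds that mix constant over time. If samples are processed by inclusion number and the mix shifts, early and late batches will differ in CAC prevalence. Held-out samples drawn from the same batches share the artefact, so the validation figure would look sound.

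The primary objective is diagnostic accuracy. Section 4.1 puts existing approaches at an AUC of 0.60–0.65, so even a modest artefact could pass for an advance.

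**Working it through.** **The plan's own figure.** The 800 cannot be reproduced. Section 9.3 rests it on experience with training and gives no error rate, target AUC or prevalence. The argument does not depend on it beyond the count of samples.

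**Inputs.** From the documents: 800 samples; a hold-out of 10–20%, that is 80 to 160 samples. Assumed, because the documents give none: number of batches (4, 9 or 17), mean CAC prevalence (50%), size of drift, and a classifier that identifies batch perfectly. The last assumption makes the results upper figures for each drift.

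**Step 1: closed form, two equal batches.** With prevalences p1 < p2 and mean P, calling the higher-prevalence batch positive gives

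- TPR = (p2/2)/P
- FPR = ((1 − p2)/2)/(1 − P)
- AUC = 0.5 + (TPR − FPR)/2

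For 40% and 60%: P = 0.5, TPR = 0.30/0.5 = 0.60, FPR = 0.20/0.5 = 0.40, AUC = 0.60. For 45% and 50%: P = 0.475, TPR = 0.25/0.475 = 0.526, FPR = 0.25/0.525 = 0.476, AUC = 0.525. Equal prevalences give 0.50.

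**Step 2: gradual drift with a hold-out.** The simulation uses 800 samples, prevalence changing linearly over enrolment, a random hold-out of about 20%, and 600 replicates. The score for a sample is the CAC prevalence of its batch in the training part. Mean hold-out AUC from batch alone:

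| Drift over enrolment | Enrolment order: 4 / 9 / 17 batches | Random allocation: 4 / 9 / 17 batches |
|---|---|---|
| none | 0.502 / 0.505 / 0.499 | 0.500 / 0.499 / 0.500 |
| 40% to 60% | 0.556 / 0.546 / 0.538 | 0.497 / 0.498 / 0.497 |
| 30% to 70% | 0.624 / 0.621 / 0.611 | 0.500 / 0.501 / 0.498 |
| 20% to 80% | 0.688 / 0.692 / 0.687 | 0.501 / 0.503 / 0.501 |

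The hold-out does not remove the artefact; random allocation does. A single hold-out is also noisy: with 9 batches in enrolment order and a 40% to 60% drift, the central 95% of replicates runs from 0.455 to 0.637. An artefact of this size could not be recognised from one validation result.

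**Step 3: added to a real signal.** Take the two-batch case at 40% and 60% with a true within-batch AUC of 0.60, and let the classifier combine both sources. A random case and a random non-case fall in favourably different batches with probability 0.6 × 0.6 = 0.36, in the same batch with 0.48, and in unfavourably different batches with 0.4 × 0.4 = 0.16. Under a binormal model, the chance that the case ranks higher is 0.968, 0.600 and 0.089 respectively. Pooled AUC = 0.36 × 0.968 + 0.48 × 0.600 + 0.16 × 0.089 = 0.651, against a true 0.60.

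**Step 4: a trap in the remedy.** If batches are forced to equal CAC counts and the hold-out is then an unstratified random draw within batches, the same simulation gives batch-only AUCs of about 0.44 (4 batches), 0.40 (9) and 0.36 (17). A batch with more cases left in training has fewer in the hold-out, so the training prevalence points the wrong way. Balance on CAC therefore does not by itself guarantee zero distortion; the split matters too.

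**The case against.** The strongest reply is that the bias needs a batch–CAC association, and the documents show none. This is one cohort, scanned on one machine, with cases and non-cases recruited together, so batches filled in order would normally hold both. Without drift the batch-only AUC is 0.50, and with small drift the effect is slight. No section says that samples will be processed by inclusion number, and section 5.1 neither calls its hold-out random nor ties it to this study. All of that stands, and it makes the risk conditional.

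A reader might infer more than the text supports in four ways:

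- **That CT results are known when samples are sequenced.** Section 7.1 gives the order of scan and sequencing, not when scores are read or locked, or who sees them.
- **That the provider is unmasked.** No masking statement exists, but the coding in section 9.1 puts no CAC result on the tube. Only enrolment order is visible.
- **That sequencing at the end is itself the fault.** It is what makes random allocation cheap. Only sequencing is said to be deferred, however; extraction and library preparation are not dated.
- **That batch effects could never be separated afterwards.** This is true only if batch and CAC are completely confounded. With partial confounding, as in all the scenarios above, a within-batch analysis can recover the true accuracy, provided batch was recorded. The plan does not provide for that record.

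It may also be said that plate layout belongs in a laboratory manual. The manual described in section 9.2 does not list it.

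**Conclusion.** The point holds as an omission with a conditional consequence. The plan has no random allocation, no batch record and no validation that could expose a batch artefact, while the method is one that can exploit such an artefact. If CAC prevalence is stable over enrolment, or if batches are not filled in order, the expected inflation is nil. If batches follow enrolment order and prevalence drifts, the AUC from batch alone is about 0.54–0.56 (40% to 60%), 0.61–0.62 (30% to 70%) or 0.69 (20% to 80%). These figures rest on assumed drifts, assumed batch counts and perfect recognition of batch; they show a range and do not predict a result. The change should be made before samples are run, because allocation cannot be altered afterwards.

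**What to change.** **Section 8.3.** Allocate samples at random to library and sequencing batches, using a list made by someone outside the laboratory and spread over recruitment setting, recruitment period and tube type. State when extraction takes place. If it is also deferred, include extraction batches in the list; if it runs during enrolment, record the extraction date. State that CT results are kept from the laboratory and the provider. Record batch, tube type and storage route for every sample. The last two matter because randomising library batches does not break a link between CAC and tube or storage.

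**Section 9.4.** Report CAC by batch, and make the validation split by whole batches. Do not use an unstratified split inside CAC-balanced batches.

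**Cost.** A plate map, a few stored fields and somewhat less freedom in choosing validation splits. No further samples or patients are needed.
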